## **8 INTERVENTION DISCONTINUATION**

Participants may decline the V-CST referral and also may withdraw voluntarily from the study at any time and for any reason without consequence. Additionally, specifications are established for discontinuing participant involvement in V-CST if ongoing involvement poses undue risk of AEs, such as if a participant is frequently combative and/or verbally abusive to other participants.

During V-CST sessions, the facilitators will observe all participants for expressions or signs of extreme stress or argumentative or confrontational behavior, such as yelling, cursing, or arguing with other participants. Facilitators will intervene when such signs are observed, such as to redirect the discussion to another topic. Participant involvement in V-CST will be discontinued temporarily or for the remainder of the study depending on the frequency and severity of the AEs and the responsiveness of the participant to redirection. Participant involvement in V-CST will be temporarily discontinued (for the remainder of the session) when more than one instance of such heightened stress is observed during a single V-CST

session. Additionally, participant involvement in the trial will be discontinued when instances of such heightened stress are observed in three separate V-CST sessions.

## **9 STATISTICAL CONSIDERATIONS**

### **9.1 General Design Issues**

Referral for V-CST is the intervention that will be introduced in this study. The study design is a two-armed, open-labeled randomized pilot ePCT to evaluate V-CST's effectiveness for promoting cognitive function in people with mild-to-moderate dementia. Clinically meaningful cognitive change will be determined based on change in scores on the MMSE, MoCA, and SLUMS, and will be compared across intervention and control groups.

### **9.2 Sample Size and Randomization**

168 people with mild cognitive impairment and/or mild to moderate dementia will be enrolled into the study, and 56 will be assigned to the intervention group through randomized allocation to receive V-CST referral, and 112 participants will be randomly allocated to the control group to receive the current standard of care (no V-CST referral). Randomization will be stratified by site by a random number sequence in a 1:2 ratio.

#### **9.2.1 Treatment Assignment Procedures**

During study enrollment, the designated Site Lead/and or RA from each participating HCS will be supported by the UMass study coordinator to generate a list of eligible participants, based on this study's inclusion criteria, and to randomize the list by a random number sequence in a 1:2 ratio to either the intervention group (V-CST referral) or control group (no V-CST referral).

The HCS Site Lead will refer eligible patients in the intervention group for V-CST. Referrals for V-CST will stop when all 56 intervention group members have been offered a referral or when all 7 V-CST groups have begun.

### **9.3 Interim Analyses and Stopping Rules**

Although no AEs are anticipated, the possibility of AEs will be monitored at every V-CST session, and specifications are established for discontinuing participant involvement in V-CST should they arise, as described above. The primary potential risk of V-CST is an increase in stress among participants, such as if participants are argumentative or confrontational with each other.

During V-CST sessions, the facilitators will observe participants for expressions or signs of increased stress or argumentative or confrontational behavior, such as yelling, cursing, or arguing with other participants. V-CST facilitators will immediately intervene when such signs are observed, such as to redirect the discussion to another topic. Participant involvement in V-CST will be discontinued temporarily or for the remainder of the treatment pending the frequency of these extreme stress instances and the responsiveness of the participant to redirection. Participant involvement in V-CST will be temporarily discontinued (for the remainder of the session) when more than one instance of such heightened stress is observed during a single V-CST session. Additionally, participant involvement in V-CST will be discontinued altogether when instances of such heightened stress are observed in more than two separate V-CST sessions.

In any V-CST group where more than one participant's involvement in V-CST is discontinued altogether due to multiple AEs, findings will be presented to the study statistician to review the events by group to determine whether there are statistical as well as clinical concerns. The statistician will report his findings to the project Safety Officer. The findings will be used to determine what steps will be taken.

## 9.4 Outcomes

Both primary and secondary outcomes will be examined, as described below.

### 9.4.1 Primary Outcome

The primary outcome to be assessed is clinically meaningful reduction in cognitive impairment. Reduction in cognitive impairment from baseline to post-intervention will be determined by comparing pre- and post-scores on standardized measures of cognition (i.e., the MOCA, SLUMS, or MMSE). A change—either increase or decrease—of 2 points or greater will indicate a clinically meaningful change. Primary outcome data will be retrieved from participating site records.

The MOCA, SLUMS, and MMSE are standardized screening tools commonly used by clinicians to determine a person's cognitive status. Although each of these instruments is relatively quick and easy to use and calculated to a total score of up to 30, each also has different sensitivity to mild cognitive impairment and length of time for completion, and clinicians use a combination of the different instruments to assess cognition rather than any one instrument exclusively. Based on prior literature, a decrease of about 1 point on each instrument is anticipated in the control group over the study period.

**MMSE** is a widely used, 12-item assessment of cognitive function that evaluates orientation to time and place, language, registration and recall of words, attention and calculation, and visual construction, and takes about 10 minutes to complete (Howland et al., 2016). MMSE assesses several areas, including orientation, immediate memory, short-term memory, and language functioning, each of which is scored independently for a total of 30 points (Slavych, 2019). MMSE has significant ceiling effects, reliably detecting dementia but not MCI (Howland et al., 2016). MMSE's brevity and ease of administration are strengths, whereas MMSE's disadvantages include its inability to detect subtle memory losses (Slavych, 2019). In a Cochrane review of CST, 10 studies involving 600 participants used the MMSE, finding the overall mean difference was 1.74 points (95% CI 1.13 to 2.36) and statistically significant ( $Z = 5.57$ ,  $P < 0.00001$ ) (Woods et al., 2012). In studies of people with stroke/transient ischemic attack, cerebrovascular disease, Tan et al (2017) and Kalmijn et al (1996) defined cognitive decline as a reduction of  $\geq 2$  points in the MMSE over two consecutive screenings from 3–6 months to 1 year.

**MoCA** takes the longest time of the three screening tools to complete, about 15 minutes. MOCA is useful with several populations and disorders, including Parkinson's disease, vascular dementia, traumatic brain injury, and others. MOCA addresses several concepts, including visuospatial/executive functions, naming, memory, attention, language, abstraction, delayed recall, and orientation, each of which is independently scored and combined for a total possible score of 30. MoCA's sensitivity as a screening tool for mild cognitive impairment, Alzheimer's disease, and dementia, and its ease of use are all strengths. The length of time required for MOCA administration is a disadvantage (Slavych, 2019). Consistent with their use of the MMSE, Tan et al (2017) also defined cognitive decline as a reduction of  $\geq 2$  points in the MoCA over two consecutive screenings from 3–6 months to 1 year. In a study of 175 subarachnoid hemorrhage patients, the minimum clinically important difference of the MoCA was 2 at 3-month follow-up (Wong et al., 2017). By calculating Reliable Change Index (RCI) confidence intervals (95%) from MoCA test-retest results, Krishnan et al (2017) identified a change of 1.73 points as representing a clinically meaningful difference in MoCA scores, a threshold beyond which the likelihood is high that an individual's change in performance reflects actual change in cognitive ability rather than noise.

**SLUMS** takes the shortest time of the three screening tools to complete, about 7 minutes. It includes 11 questions addressing several concepts—orientation, short-term memory, calculations, naming of animals, clock drawing test, recognition of geometric figures—and each response gets scored for a total of 30. The brevity of the SLUMS and its sensitivity for mild cognitive impairment are strengths. Limited research regarding psychometric properties of the SLUMS and its use with different populations are disadvantages (Slavych, 2019). Stewart et al (2017) compared pre-/post-CST SLUMS scores with 40 participants and found on average scores were 1.78 points higher after the intervention.

The study will leverage the use of these three instruments in standard practice to evaluate the primary outcome, clinically meaningful cognitive change, among patients who are assessed with any of the three different instruments. Clinically meaningful cognitive change will be determined based on a 2-point change in scores on the three instruments from pre- to post-treatment. Additionally, distribution-based analysis to determine clinically meaningful cognitive change is described in section 9.5.

Another potential indicator of meaningful change is the clinical decision to utilize an alternate cognitive assessment at post-intervention due to the presence of a ceiling or floor effect of the assessment originally utilized at pre-intervention. Based on input from clinicians participating in this study, pre- to post-intervention change from using the MoCA or the SLUMS to using the MMSE will initially be used to indicate a clinically meaningful *reduction* in cognitive function, and a change from using the MMSE to the MoCA or SLUMS will initially be used to indicate a clinically meaningful *improvement* in cognitive function. Any such *reductions* or *improvements* in cognitive function determined based on change in instrument use will be verified by the study coordinator directly with the HCS.

#### 9.42 Secondary Outcomes

Because some trials have shown improvement in cognitive function for V-CST compared to control procedure, we will also compare the proportion of participants who experience clinically meaningful improvement in cognitive function between the two arms.

The other two secondary outcomes to be assessed through each site's pre- and post-intervention EHR data review for the intervention and control groups is the prescription of new psychotropic medications or the change in dosage of psychotropic medications. These secondary outcome study hypotheses are that fewer intervention than control group members will be newly prescribed psychotropic medications or have an increase in dosage of these medications. Study data on psychotropic medications will be retrieved from participating site records.

The following process measures also will be calculated using data from V-CST facilitators to assess trial feasibility:

- Referral acceptance rate at each health care setting (the percentage of PLWD in the intervention group who are referred for V-CST);
- Enrollment rate (the percentage of PLWD referred for V-CST who enroll in V-CST)
- V-CST adherence, which will be measured by monitoring participant attendance at V-CST sessions and calculating the percentage of sessions attended by enrolled participants;
- V-CST attrition, which will be assessed by documenting when participants cease attending V-CST between session 1 (S1) and session fourteen (S14).

To support quality improvement in these process measures, adherence and attrition also will be examined qualitatively when they occur. Specifically, when enrolled participants do not attend V-CST sessions, or when they cease attending V-CST sessions altogether, the intervention delivery team will inquire via email with the individual to query the reason(s) for their missed attendance or attrition. Additionally, in

the case of attrition, the HCSs will be notified, and the sites will inquire about the reasons for attrition at the patient's next regularly scheduled appointment. Participants' reasons for adherence and attrition will be reported to the PI, study coordinator, and/or lead facilitator as they are identified to continuously inform CST delivery and to determine any refinements that may be needed for successfully delivering CST online.

Finally, participants in V-CST will complete three measures in conjunction with an orientation session prior to S1 and a close-out session after S14 as these assessments are conducted in standard V-CST programming: Geriatric Depression Scale (GDS), Engagement and Independence in Dementia Questionnaire (EID-Q) – Subscales 3-5, Positive Psychology Outcome Measure (PPOM). Results at both time points will be summarized in reports for participating sites to share with participants.

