#### **4.1 Inclusion Criteria**

Participants must meet all the inclusion criteria to participate in this study, to be assessed in clinic or by record review at each site:

- Diagnosis of Mild Cognitive Impairment or Mild to Moderate Dementia
- MoCA score of 10 to 26 OR SLUMS score of 10 to 26 OR MMSE score between 13 and 24 recorded as present  $\leq$  24 months before the record review
- English-speaking
- Visit expected to be scheduled to include cognitive screening 6 to 12 months after record review.

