### Randomization:

The UMB team will de-identify and sort screening log and create an enrollment log with each participant assigned a unique study identifier for randomization. Participants will be allocated by a random number sequence in a 1:2 ratio into the intervention or control arms within each site. The study biostatistician will create the random sequence that the HCSs will apply for the random allocation of participants. The sequence will be created using block randomization with size of 4 to ensure balance across time.

At each HCS, clinicians will offer referral for V-CST to participants who were randomly assigned to the intervention group. The referring physician will meet the patient in clinic or contact the patient by phone to offer the referral. The referral will describe what participation entails, including the schedule of V-CST sessions, the use of the online meeting platform, and the expectations of participants' caregivers. To be consistent with real-world clinical practice, blinding will not be used (Dal-Re et al., 2018): the referral

sites will make referrals to the V-CST facilitator team following standard treatment referral protocols, which include the names and contact information of the patients who will be referred.

Patients who are referred for V-CST will be contacted by CaringKind using their standard procedures to enroll referred patients in V-CST.

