## 6.1 Schedule of Evaluations

Assessment	Pre-Treatment Data Screening (Day -90 to -30)	Treatment Enrollment (Day -30 to -1)	Treatment Group 1-7 (Day 0 to 200)	Post-Treatment Data Screening (Day 61 to 275)
Inclusion/Exclusion criteria	X			
Randomization	X			
Demographics	X			
Diagnoses	X			
Medications	X			
Cognitive function	X			X
Referral acceptance rate	X			
Enrollment rate		X		
Attendance			X	
Attrition			X	
Therapy administration form			X	
Weekly Monitoring Participant Progress reports			X	
Adverse Events			X	

NOTE: Day 0 = Date of V-CST Group 1, Session 1

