### **6.2.4 Post-V-CST Data Screening**

Post-V-CST data screening will be conducted by the referring physician after the 14 V-CST sessions have been held.

At this time, post-intervention data on medications and cognitive screening scores will be abstracted from HCS records on the study participants. Post-treatment data screening will conclude with HCSs uploading the abstracted data to the project Sharepoint file.

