### **10.2 Data Management**

Data from the HCSs will be gathered through a targeted raw data pull that includes only select information about study participants from the EHRs. First, clinical sites will retrieve patient data from their records based on the study inclusion/exclusion criteria, including demographic information, medications, diagnoses, and cognitive function (MoCA, SLUMS, and/or MMSE).

The research sites Yale and UConn will share data directly with UMass via Sharepoint, and will include data on V-CST enrollment, attendance, attrition, fidelity to the treatment administration manual, adverse events, and three measures standardly collected before and after participation in V-CST, the Geriatric Depression Scale, Engagement and Independence in Dementia Questionnaire - Subscales 3-5, and the Positive Psychology Outcome Measure. CaringKind will provide patient data to the referring HCS physician per standard of care. Once data is securely transferred to UMass, all study data will be stored in Microsoft Teams which is a HIPAA compliant password protected server only accessible to the UMass research team.

Confidentiality of participant records will be maintained by HCSs uploading all data to a secured server in a Sharepoint file. Access to the Sharepoint file will be limited to the PI and study coordinator at UMass, who will clean and deidentify data and assigning a unique study identifier for each participant. The UMass team will maintain a de-identified and PHI enrollment internally for communication between the research sites to ensure HIPAA compliance and protection against loss of confidentiality. UMass will be the primary location for all data management, maintenance, and distribution. All data will then be transferred from Sharepoint into MS teams to be maintained and clean accessible to only the UMass team. Sharepoint will only be used to transfer data and will not be the primary storage platform. MS teams is a HIPAA compliant and password protected platform maintained and stored on a UMass IT server. The de-

identified data will be transferred it to the study biostatistician at Brown University in an encrypted email. Using the deidentified data provided by UMass, [name], study biostatistician, will conduct data analysis, interpret results, and report findings to the PI also through encrypted email messaging.

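### Nothing in the plan shields the testing, abstraction or coding of the follow-up cognitive score from knowledge of arm

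*Combined protocol and SAP*

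**What the plan says.** The primary outcome is a change of 2 points or more on the MoCA, SLUMS or MMSE, taken from routine clinic records (Section 9.4.1). The follow-up score comes from an ordinary visit; Section 4.1 requires "Visit expected to be scheduled to include cognitive screening 6 to 12 months after record review".

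Four provisions bear on who knows the arm when that score is produced and processed:

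- **Referral (Section 4.3).** "The referring physician will meet the patient in clinic or contact the patient by phone to offer the referral". The same section states: "To be consistent with real-world clinical practice, blinding will not be used". Site clinicians also keep a screening log that records each patient's arm.
- **Dropout inquiry (Section 9.42).** The site is told of attrition, and then "the sites will inquire about the reasons for attrition at the patient's next regularly scheduled appointment".
- **Abstraction (Section 6.2.4).** "Post-V-CST data screening will be conducted by the referring physician after the 14 V-CST sessions have been held". Cognitive scores are among the items abstracted. Section 10.2 adds: "CaringKind will provide patient data to the referring HCS physician per standard of care".
- **Instrument switches (Sections 9.4.1 and 9.5).** A move from MoCA or SLUMS to MMSE counts initially as decline, and a move from MMSE to MoCA or SLUMS as improvement. Section 9.5 compares such cases with the actual scores and then asks the referring physician to verify them.

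No section provides a masked tester, a masked abstractor, a rule for choosing among several follow-up scores, or a lock on outcome coding before arm is merged.

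**The concern.** The cut-off is 2 points, and Section 9.4.1 expects control patients to lose about 1 point, so many patients will sit close to the line. A small difference between arms in how the test is given, which score is taken or how a switch is judged would reclassify patients in one arm only. Neither randomization nor intention-to-treat analysis protects against that. H1 and H2 rest on the same scores, so both would be affected.

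The dropout inquiry is one visible route. It concerns intervention patients only, and it may take place at the visit where the endpoint is measured. Switch verification leaves the most room for judgment, because a physician who knows the arm is asked to confirm whether a primary-endpoint event occurred. Abstraction of a single recorded total leaves little discretion. Where several scores exist there is more, since no selection rule is given.

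**Working it through.** **Can the inquiry and the test fall at one visit?** Section 6.1 runs the V-CST groups from Day 0 to 200 and the post-treatment window from Day 61 to 275, so the two periods overlap. Visit frequency is not given. Coincidence is possible but not certain.

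**Inputs from the documents.** 56 intervention and 112 control participants (Section 9.2). A 50% decline rate, a 22% decrease, 80% power and a 5% level (Section 9.5).

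**Assumed inputs, not in the documents.** SD of change 2, 3 or 4 points; a drift of 0.5 point; V-CST attrition of 10% to 30% of the intervention arm.

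**Step 1: the plan's own figure.** Read as 50% versus 28%, two-sided, pooled test:

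- pooled rate = (56 × 0.28 + 112 × 0.50)/168 = 0.4267
- SE0 = √[0.4267 × 0.5733 × (1/56 + 1/112)] = 0.0809
- SE1 = √[0.28 × 0.72/56 + 0.50 × 0.50/112] = 0.0764
- power = Φ[(0.22 − 1.96 × 0.0809)/0.0764] = 78.9%

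This agrees with the stated 80%. A relative reading (50% to 39%) gives 26.7%, so the 22% is an absolute difference. The power statement is not in question.

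**Step 2: drift across the whole intervention arm, no true effect.** Control rate 50%; intervention rate p1 = Φ(−0.5/SD). With d = 0.50 − p1, the chance of a significant result favouring V-CST is Φ[(d − 1.96 × SE0)/SE1], with both standard errors recomputed at p1. With no drift it is 2.5%.

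| SD | p1 | Fall in decline rate (points) | Share of 22 points | Chance of false result favouring V-CST |
|---|---|---|---|---|
| 2 | 40.1% | 9.9 | 45% | 22% |
| 3 | 43.4% | 6.6 | 30% | 12% |
| 4 | 45.0% | 5.0 | 23% | 9% |

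A second model, with mean change −1 and decline scored at or below −1.5 before rounding, gives falls of 9.3 to 4.9 points for SD 2 to 4.

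**Step 3: the same drift in V-CST dropouts only.** With attrition a, the fall is a × [0.50 − Φ(−0.5/SD)].

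- Smallest: 0.10 × 5.0 = 0.5 point; chance of a false result favouring V-CST 2.9%.
- Largest: 0.30 × 9.9 = 3.0 points; chance 5.5%.

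**Step 4: the opposite direction.** Suppose the true rates are 28% and 50%, and 25% of the dropouts' non-declines are recorded as declines. Then p1 = 0.28 + 0.72 × a × 0.25. At a = 10%, p1 = 29.8% and power falls from 78.9% to 71%. At a = 30%, p1 = 33.4% and power falls to 53%.

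**The case against.** The strongest reply is that this is a declared pragmatic design. Open label is stated with a reason, outcomes are deliberately routine-care data, and Section 10.1 says the main purpose of specifying outcome measurement is to show that it can be collected pragmatically. That stands for referral and care. It does not extend to abstraction and coding, which are research tasks and can be masked without touching practice.

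Three stronger readings are tempting, and the documents do not support them.

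- A reader might infer that the dropout inquiry by itself could produce a 9-22% chance of a false result. It could not on these assumptions: those figures need drift in all 56 intervention patients, and the inquiry reaches only those who stopped V-CST.
- A reader might infer that the individual who made the referral gives the test and personally pulls the score. The tester is not named, and the Operational Definitions treat the health care system and its referring physicians as equivalent, so Section 6.2.4 may mean the site.
- A reader might infer a bias in favour of V-CST. Nothing fixes the direction; a tester could as easily mark down a patient who quit, as Step 4 shows.

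It is also fair to say that putting the test before the inquiry does not blind a tester who already knows the arm from the referral or the attrition notice. It removes only the prompt at the visit.

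**Conclusion.** The point holds as a gap in protecting the endpoint. Nothing in the plan keeps knowledge of arm away from the testing, abstraction or coding of the follow-up score, and the stated reason for not blinding does not cover the last two. Its possible size ranges from small (0.5 to 3.0 points through the dropout inquiry alone) to material (5.0 to 9.9 points, or 23% to 45% of the planning difference, if drift affects the whole arm). All of these figures rest on an assumed drift and SD, and those for the inquiry also on assumed attrition. They show sensitivity and do not predict that bias will occur. The change is worth making because it costs little and because the pilot is meant to show whether this design can test H1.

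**What to change.** 1. **Section 9.42.** State that where the appointment includes cognitive screening, the test is completed and its total recorded before V-CST or dropout is raised.
2. **Section 6.2.4.** Have scores abstracted by existing staff who took no part in assignment or referral, from a list without the arm column. Section 9.2.1 lets the site research assistant randomize the list, so that role does not qualify automatically. Take the first cognitive score in the follow-up window whatever the instrument, so that the instrument-switch rule is kept. Define the start of the window by one rule for both arms, because Section 6.1 counts days from the first session of Group 1.
3. **Section 9.5.** Code decline and improvement, including switch cases checked against Table 1, and lock the coding before arm is merged. Table 1 has no SLUMS column, so switches involving SLUMS need a rule written beforehand. Where physician verification is kept, record it separately and report H1 with and without the physician-verified switch cases.

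Open-label referral and care are unchanged. The cost is a fixed order within one visit and a reassigned abstraction task. Masking will be incomplete if chart notes show the referral. Section 4.3 says enrollment and randomization are complete, so some follow-up visits may already have taken place; parts 2 and 3 can still be applied.
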